#### **5.3 Dose Escalation and Stopping Rules**

The dose-limiting toxicity (DLT), as defined in Section 5.5, will be the basis for determining the maximum tolerated dose (MTD). Any subject who receives at least one dose of the study drug (BKM120) will be included in analysis for DLT. Treatment cohorts will be dosed in escalating order, as outlined in Table 8, only after the safety of the previous dose level has been established, or until an MTD has been determined.

Subsequent dose levels will be opened for treatment as follows:

1) Escalation to the subsequent dose level will occur only after all subjects in the previous cohort have completed the full 7-week course of BKM120-CRT and have been evaluated for safety and toxicity. Safety will be evaluated based on the incidence of adverse events (AEs), physical exam findings, and clinical laboratory test results. A review of the safety data for each cohort will be conducted when all of the above data are available. In the event that an MTD is not reached after dose level 5, the study will be considered to have reached a biologically acceptable dose appropriate for Phase II study. Any further dose escalations or de-escalations will require a protocol amendment.

2) Three patients will initially be enrolled at dose level 1. The following rules apply for the advancement to the next dose level and to determine the MTD (see also Table 7). Enrollment may proceed at the higher dose according to the rules after three patients have been treated for the 2 weeks of BKM120 followed by 7 weeks of BKM120+CRT at a given dose level and safety data have been reviewed. The dose will be increased until a DLT is observed in one subject. Dose limiting toxicity is graded according to the National Cancer Institute’s CTCAE v4.0 (<http://ctep.cancer.gov/forms/CTCAEv4.pdf>).

Once a DLT occurs, additional subjects will be added to the cohort until either a second subject experiences a DLT or six subjects are treated at that dose level. If no additional subject experiences a DLT at the trigger dose-level, further dose escalation as outlined in Table 8 will be explored in cohorts of three subjects.

If two or more subjects experience a DLT at a given dose, then three additional subjects will be treated at the next lower dose, unless six subjects have already been treated at that dose.

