#### **5.5 Dose-Limiting Toxicity**

Toxicity will be assessed using the NCI Common Toxicity Criteria for Adverse Events, version 4.0

[http://evs.nci.nih.gov/ftp1/CTCAE/CTCAE\\_4.03\\_2010-06-14\\_QuickReference\\_8.5x11.pdf](http://evs.nci.nih.gov/ftp1/CTCAE/CTCAE_4.03_2010-06-14_QuickReference_8.5x11.pdf) unless

otherwise specified (e.g., hyperglycemia). A dose-limiting toxicity (DLT) is defined as an adverse event or abnormal laboratory value assessed as unrelated to disease, disease progression, inter-current illness, or concomitant medications, and occurs < 28 days following the last dose of BKM120, and meets any of the criteria listed in Table 9.

Whenever a patient experiences toxicity that fulfills the criteria for a DLT (or a potential DLT), treatment with BKM120 will be interrupted (if not otherwise specified) and the toxicity will be followed up as described in section 5.3. Exceptions are CTCAE grade 2 hyperglycemia and CTCAE grade 2 mood alteration, where BKM120 treatment will be continued under appropriate co-medication. The criteria for dose-limiting toxicities are outlined in Table 9.

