**Table 9: Criteria for Defining Dose-Limiting Toxicities**

TOXICITY	ANY OF THE FOLLOWING CRITERIA
Hematologic a	≥ CTCAE grade 3 neutropenia for > 7 consecutive days
	CTCAE grade 3 thrombocytopenia for > 7 consecutive days
	CTCAE grade 4 thrombocytopenia
	Febrile neutropenia (ANC < 1.0 x 10  /L, fever ≥ 38.5°C)
Renal	Serum creatinine ≥ 2.0 x ULN to ≤ 3.0 x ULN for > 7 consecutive days
	> CTCAE grade 3 serum creatinine
Hepatic b	Total bilirubin ≥ 2xULN to ≤ 3.0 x ULN for > 7 consecutive days
	> CTCAE grade 3 total bilirubin
	CTCAE grade 3 AST or ALT for > 7 consecutive days
	CTCAE grade 4 AST or ALT
Endocrine	Grade 2 hyperglycemia (confirmed with a repeat FPG within 24 hours) that does not resolve to grade 0 within 14 consecutive days (after initiation of glimepiride, metformin or glibenclamide)
	≥ Grade 3 hyperglycemia (confirmed with a repeat FPG within 24 hours)
Metabolic/Laboratory	CTCAE grade 3 asymptomatic amylase and/or lipase, not reversible to ≤ CTCAE grade 2 for > 7 consecutive days
	CTCAE grade 4 asymptomatic amylase and/or lipase
Pancreatitis	≥ CTCAE grade 2
Cardiac	Cardiac toxicity ≥ CTCAE grade 3 or cardiac event that is symptomatic or requires medical intervention
	Clinical signs of cardiac disease, such as unstable angina or myocardial infarction, or Troponin ≥ CTCAE grade 3
Neurotoxicity	≥ 1 CTCAE grade level increase
Mood alteration	CTCAE grade 2 mood alteration that does not resolve to ≤ grade 1 within 14 days despite medical treatment (for Anxiety only, if worsened from baseline)
	≥ CTCAE grade 3 mood alteration
Dermatologic	Any phototoxicity ≥ CTCAE grade 2, or skin toxicity (rash) resulting in interruption of BKM120 for > 21 consecutive days
Other adverse events	≥ CTCAE grade 3 adverse events (excluding ≥ CTCAE grade 3 elevations in

	alkaline phosphatase)
	≥ CTCAE grade 3 vomiting or CTCAE grade 3 nausea despite the use of standard anti-emetics
	≥ CTCAE grade 3 diarrhea despite the use of optimal anti-diarrhea treatments
	CTCAE grade 3 fatigue (asthenia) for > 7 consecutive days CTCAE grade 4 fatigue (asthenia)

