#### 5.12.1.4 Serum chemistry

Biochemistry includes the following parameters: K+, Na+, Ca++, Mg++, LDH, ALT, AST, total bilirubin (direct and indirect), creatinine, amylase, GGT, lipase, alkaline phosphatase (fractionated if alkaline phosphatase is grade 2 or higher), bicarbonate, phosphorus, uric acid, total cholesterol, HDL, LDL, triglycerides, glucose, urea or BUN, albumin, and total protein are required at baseline and at end of treatment. Subsequent assessments always include K+, Na+, Ca++, ALT, AST, total bilirubin (direct and indirect), creatinine, alkaline phosphatase, bicarbonate, phosphorus, glucose, urea or BUN, albumin, and total protein BUT, lipase, total cholesterol, HDL, LDL, triglycerides should be obtained.

Because accurate serum glucose and lipid measurements are required, patients should be fasting at the time of the blood sampling.

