 Serum chemistry - K+, Na+, Ca++, Mg++, LDH, ALT, AST, total bilirubin (direct and indirect), creatinine, amylase, GGT, lipase, alkaline phosphatase (fractionated if alkaline phosphatase is grade 2 or higher), bicarbonate, phosphorus, uric acid, total cholesterol, HDL, LDL, triglycerides, glucose, urea or BUN, albumin, and total protein are required at baseline and at end of treatment. Subsequent assessments always include K+, Na+, Mg++, Ca++, ALT, AST, total bilirubin (direct and indirect), creatinine, alkaline phosphatase, bicarbonate, phosphorus, glucose, urea or BUN, albumin, and total protein BUT, lipase, total cholesterol, HDL, LDL, triglycerides should be obtained on Day 1 of CRT and EOT  Coagulation - PT or INR, PTT: Day 1 of CRT and EOT

 Patients must be fasting overnight for at least 8 hours. Additional measurements may be performed as clinically indicated.

 Patients will be assessed weekly for adverse events for the duration of the treatment (2 weeks of BKM120 and 7 weeks of BKM120+CRT = 9 weeks) and every 2 weeks after conclusion of BKM120+CRT (EOT) during the first month, then monthly for 3 months, then every 3 months, until first progression, death, or 2 years post study entry whichever occurs first.

 Follow up (FU) will take place every 2 weeks after conclusion of BKM120+CRT (EOT) during the first month, then monthly for 3 months, then every 3 months, until first progression, death, or 2 years post study entry whichever occurs first. Follow up visits must occur within +/- 14 days of the protocol specified date.

 After first progression, patients will be followed for survival every 3 months until 2 years post study entry.

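### Asymptomatic lipase and amylase elevations count as DLTs, but the calendar leaves about seven weeks between on-treatment lipase draws, and its chemistry row contradicts the weekly liver and creatinine testing required elsewhere

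*Combined protocol and SAP*

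**What the plan says.** Table 9 has two rows for asymptomatic pancreatic enzymes: "CTCAE grade 3 asymptomatic amylase and/or lipase, not reversible to ≤ CTCAE grade 2 for > 7 consecutive days" and "CTCAE grade 4 asymptomatic amylase and/or lipase". The second has no duration condition. Section 5.5 counts an event that "occurs < 28 days following the last dose of BKM120", so the DLT window covers the nine treatment weeks and nearly four more. Section 5.3 states: "Any subject who receives at least one dose of the study drug (BKM120) will be included in analysis for DLT".

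The study calendar is Table 17 in Section 10 (Appendix B has another Table 17, which lists CYP3A drugs). Its serum chemistry row is ticked at screening, CRT Day 1 and EOT only. Footnote 6 asks for the full panel, including amylase and lipase, at baseline and end of treatment. Of the other visits it says "Subsequent assessments always include K+, Na+, Mg++, Ca++, ALT, AST, total bilirubin (direct and indirect), creatinine, alkaline phosphatase, bicarbonate, phosphorus", and the list continues without amylase. For lipase it adds: "lipase, total cholesterol, HDL, LDL, triglycerides should be obtained on Day 1 of CRT and EOT". Section 5.12.1.4 repeats the panel but stops at "total protein BUT, lipase, total cholesterol, HDL, LDL, triglycerides should be obtained", with no time points.

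The part of Section 7.1 on managing liver toxicities requires weekly monitoring. Section 6.1 requires weekly serum creatinine within 24 hours of cisplatin.

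**The concern.** An asymptomatic laboratory DLT exists for the trial only if someone draws the blood. Because every dosed subject is in the DLT analysis, a patient whose elevation falls between draws is counted as DLT-free. In a 3+3 design one event decides the next step. Under Table 7, a missed DLT turns 1 of 3 (enter three more) into 0 of 3 (escalate), or 2 of 6 (stop) into 1 of 6 (escalate).

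There is also a patient-safety side. Section 5.5 says that for a DLT or potential DLT "treatment with BKM120 will be interrupted (if not otherwise specified) and the toxicity will be followed up". That cannot happen before the value is known, so dosing could continue for weeks with a qualifying elevation present.

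The second strand is consistency. A site that works from the calendar would draw chemistry at one of the nine weekly visits before EOT, although the text requires liver tests every week and creatinine with each cisplatin dose. Those results feed the hepatic and renal DLT rows.

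**Working it through.** **Section 13 figures.** With true DLT rate p, the probability of escalation is (1−p)³ + 3p(1−p)²·(1−p)³. For p = 20, 30, 40, 50 and 60% this gives 0.709, 0.494, 0.309, 0.172 and 0.082, matching the stated .71, .49, .31, .17 and .08. These figures are correct; they take every DLT as observed.

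**Counting draws.** The weekly visits before EOT are BKM120 Days 1 and 8 and CRT Days 1, 8, 15, 22, 29, 36 and 43, nine in all.
- Chemistry row: ticked at 1 of 9 (CRT Day 1), then EOT. For creatinine, that is 1 of the 7 cisplatin visits.
- Lipase: CRT Day 1 and EOT.
- Amylase: EOT only if footnote 6 is read literally; CRT Day 1 and EOT if the tick means the full panel.
- After EOT: no chemistry.

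**Looking for draws elsewhere.** Section 5.12.9 speaks of regular chemistry monitoring without a frequency. Section 10 repeats laboratory tests when a participant is deteriorating, which an asymptomatic rise need not trigger. Table 10 repeats start only after a grade 3 value has been found. The allowance for extra measurements sits in footnote 8, on fasting glucose. None supplies a routine enzyme draw.

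**Length of the gap.** BKM120 starts two weeks before CRT, so CRT Day 1 is study day 15. Treatment lasts 9 × 7 = 63 days. The calendar gives EOT no day number. Taking it as day 63, the gap is 63 − 15 = 48 days, about seven weeks.

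**Illustration (assumptions, not data).** Let onset be uniform over study days 1 to 63, a span of 62 days, with a continuous elevation of d days. Lipase draws on days 15 and 63 split the span into 14 and 48 days. The chance that a draw falls within the elevation is [min(d,14) + min(d,48)] / 62.

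| d (days) | Calculation | Detected |
|---|---|---|
| 10 | (10+10)/62 | 32% |
| 14 | (14+14)/62 | 45% |
| 21 | (14+21)/62 | 56% |
| 28 | (14+28)/62 | 68% |
| 48 | (14+48)/62 | 100% |

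With draws at the nine weekly visits (study days 1, 8, …, 57) and EOT, no gap exceeds 7 days, so detection is 100% for every row.

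Sensitivity at d = 14:
- Onset only in the lead-in: 14/14 = 100%. Onset only during CRT: 14/48 = 29%.
- EOT on day 64: (14+14)/63 = 44%; a day-by-day count gives 43%.
- Amylase drawn at EOT only: 14/62 = 23%.

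**Delay for an elevation that persists until drawn.** The mean is (14²/2 + 48²/2)/62 = 1,250/62 = 20.2 days, at most 48. With weekly draws there are eight 7-day gaps and one of 6: (8 × 24.5 + 18)/62 = 3.5 days, at most 7.

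**The case against.** The strongest reply is that the lipase schedule looks deliberate. Footnote 6 separates tests repeated at every later assessment from lipase and lipids, and the CRT Day 1 draw follows two weeks of BKM120 alone, when Section 2.2.8.8 expects steady state. That explains the schedule but does not make it fit the DLT rule, which runs through CRT and beyond.

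Several points do lower the priority. Entry requires amylase and lipase at or below the upper limit of normal and excludes pancreatitis. Symptomatic pancreatitis has its own DLT row, and adverse events are assessed weekly. Section 2.2.8.2 names no enzyme DLT in the first-in-human study, and Table 2 lists no enzyme term; however, that table shows only events above 15%, so it does not establish a rate of zero. Escalation waits until the whole cohort has finished and been evaluated, so an elevation still present at EOT is drawn before the decision. The count is at risk only where the qualifying course passes unseen.

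On the other side, pancreas findings are reported in dogs and rats (Section 2.2.6) and in mice (Section 7.1.1.3).

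A reader might infer that liver and renal toxicity go unmonitored. The documents do not support that: weekly testing is explicitly required, so this strand is a calendar error.

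**Conclusion.** The point holds. The protocol defines an asymptomatic enzyme DLT that its calendar cannot reliably detect: two on-treatment lipase draws about seven weeks apart, and at most one amylase draw before EOT. Transient elevations can be counted as no DLT, and persistent ones can be found weeks late with BKM120 continued. The serum chemistry row is also wrong against Sections 6.1 and 7.1.

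A reader might go further and conclude that the MTD will be biased upward by some amount, or that the Section 13 escalation probabilities are wrong. The documents support neither. They give no human rate, onset or duration for these elevations, and the Section 13 figures reproduce. The 45% figure rests on assumed uniform onset, a 14-day duration and EOT at day 63; restricting onset to the lead-in or to CRT moves it between 100% and 29%. The structure of the gap needs no such assumption. Priority is moderate to low.

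**What to change.** In Table 17 of Section 10, tick serum chemistry at every weekly treatment visit from BKM120 Day 1 to EOT. In footnote 6, add lipase to the tests repeated at every assessment, leaving only the lipids at CRT Day 1 and EOT. Give Section 5.12.1.4 the same list and timing. This also brings the calendar into line with the weekly liver and creatinine requirements.

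State which restart rule applies after an enzyme elevation. Table 10 allows re-treatment at grade 2 or below. Table 11 has no enzyme row, and its generic non-hematological row requires grade 1 or below. The enzyme-specific rule in Table 10 should govern.

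The direct cost is a calendar amendment and a few assays on blood already taken weekly for hematology and fasting glucose. The downstream cost is larger. Each grade 3 or higher value found brings repeats at 2 to 4 days and at 7 days, then twice weekly, imaging within one week, and interruption of BKM120. More true DLTs may be counted, so escalation may stop earlier.

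Two additions are options for the sponsor, not part of the fix:
- Weekly amylase. The parotids are irradiated, so an isolated rise might be salivary, which is an assumption from general physiology. It would need a Table 9 note on checking the source before counting a DLT.
- One chemistry draw at the first post-EOT visit. The ±14-day window lets a two-week visit slip to day 28, outside the DLT window, so the draw would need a tighter window.

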### **5. TREATMENT PLAN**

#### **5.1 Treatment Regimen**

The investigational therapy used in the course of this study is BKM120. Treatment with BKM120 starts 2 weeks prior to cisplatin and radiotherapy and continues until the end of radiotherapy.

Study medication will be self-administered by the patients continuously throughout radiation. In order to assure compliance with protocol procedures drug administration will be thoroughly explained to the patients. During the study, BKM120 will be administered orally. It is given every day including weekend days. Administration of BKM120 stops with the end of radiotherapy. If radiation is held due to toxicity, BKM120 and cisplatin will be held as well. If cisplatin is held due to toxicity, BKM120 and radiation will continue. If BKM120 is held due to toxicity, cisplatin and radiation will continue. Medication labels will comply with US legal requirements and be printed in English. The storage conditions for study drug will be described on the medication label.

BKM120 will be provided by Novartis Pharmaceuticals free of charge. BKM120 is formulated as capsules for oral administration of 10mg and 50mg strength. Capsules are packaged in bottles. BKM120 capsule cannot be crushed and has to be swallowed. It cannot be given via enteral feeding tube.

If vomiting occurs, no attempt should be made to replace the vomited dose.

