## 5.6 Follow-up for dose-limiting toxicities

Patients whose treatment is interrupted or permanently discontinued due to an adverse event or clinically significant laboratory value, must be followed as outlined in Table 10, at least once a week for 4 weeks, and subsequently at 4-week intervals, until resolution or stabilization of the event, whichever comes first. If a patient requires a dose delay of > 14 days from the intended day of the next scheduled dose, then the patient should be discontinued from the treatment but will only come off study if dead or due to refusal to continue on the study. All patients must be followed for adverse events and serious adverse events for 28 days following the last dose of BKM120.

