**Table 17: Evaluation and visit schedule**

Examination	Screening/ Baseline	BKM120 alone phase		Chemo (cisplatin) – radiotherapy (CRT)							EOT	FU until first progression 	After first progression 
		1	8	1	8	15	22	29	36	43			
Day of treatment	-21	1	8	1	8	15	22	29	36	43	EOT	FU until first progression 	After first progression 
Informed consent	X												
Medical History	X												
Inclusion/exclusion criteria	X												
Serum Pregnancy Test (within 72 hours of first treatment for WOCBP)	X	as clinically indicated											
Urinalysis	X			X							X		
Vital signs	X	X	X	X	X	X	X	X	X	X	X	X	
Physical examination (including skin rash assessment)	X	X	X	X	X	X	X	X	X	X	X	X	X
Performance Status ECOG	X	X	X	X	X	X	X	X	X	X	X	X	
Neuro-psychiatric assessment (self rating mood questionnaire) 	X	X	X	X	X	X	X	X	X	X	X	X	
MUGA/ECHO 	X			X							X		
12-lead ECG	X												
Dental Evaluation	X												
Chest X-Ray 	X			X							X		
Radiological tumor assessment/response assessment 	X											X 	
Hematology 	X	X	X	X	X	X	X	X	X	X	X		
Serum Chemistry 	X			X							X		
Coagulation Profile 	X			X							X		
Fasting plasma glucose 	X	X	X	X	X	X	X	X	X	X	X		
Adverse events 		X	X	X	X	X	X	X	X	X	X	X	

*Placement of a PEG is highly recommended prior to beginning BKM120 CRT. It is recommended that this procedure be performed prior to beginning BKM120 CRT or within the first two weeks of therapy.*

 PHQ-9 and GAD-7 questionnaires will be completed until 1 year post treatment

 MUGA/ECHO screening, Day 1 of BKM120+CRT and EOT

 A Chest X-Ray should be performed for all patients at screening, Day 1 of CRT and EOT

 Screening radiological assessments should be performed within 4 weeks prior to study entry. Radiological tumor assessments should subsequently be performed at 3 months post BKM120+CRT. Follow up imaging after the three month assessment will be at the discretion of the treating oncologist and performed when necessary. Imaging modality (PET/ CT or CT) is at the discretion of the treating oncologist.

 Hematology - WBC plus differential (neutrophil including bands, lymphocyte, monocyte, eosinophil, basophil and other counts, hemoglobin and platelets. Should be performed on screening, before each BKM120 dose; and EOT

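### For patients who finish BKM120 at or near EOT, Section 10 guarantees no visit and Table 17 schedules no laboratory test in the 27 post-treatment days that the DLT definition covers

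*Combined protocol and SAP*

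**What the plan says.** Section 5.5 counts an event as a DLT if it "occurs < 28 days following the last dose of BKM120" and meets a Table 9 criterion. Section 5.1 states: "Administration of BKM120 stops with the end of radiotherapy". For a patient who completes treatment, days 1-27 after EOT are therefore inside the definition.

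Table 17, footnote 10, sets the visits: "Follow up (FU) will take place every 2 weeks after conclusion of BKM120+CRT (EOT) during the first month". The same footnote, and the text of Section 10, give every follow-up visit the same tolerance: "Follow up visits must occur within +/- 14 days of the protocol specified date".

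Table 17 marks hematology and fasting plasma glucose at 11 time points, from screening to EOT. It marks serum chemistry at screening, day 1 of CRT and EOT. All three cells are blank in the follow-up column, which holds vital signs, physical examination, performance status, mood questionnaires, imaging and adverse events. Footnote 5 says of hematology: "Should be performed on screening, before each BKM120 dose; and EOT". For glucose after EOT there is only footnote 8: "Additional measurements may be performed as clinically indicated".

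Four other places bear on this period:

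- Section 5.6 (repeated in 5.7): "All patients must be followed for adverse events and serious adverse events for 28 days following the last dose of BKM120". It names no visit day and no test for this.
- Section 5.8.1 mentions a follow-up visit 28 days after the last dose.
- Section 5.12.9 sets a ±2-day tolerance for safety assessments, including blood tests, and has adverse events evaluated continuously.
- Section 5.3 opens the next dose level once the cohort has completed the 7-week course and been evaluated for safety. Table 7 heads its count as DLTs in the treatment period.

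**The concern.** The primary endpoint is the MTD, and Section 5.3 bases it on DLTs as defined in Section 5.5. Several Table 9 criteria are laboratory values that can be silent: grade 4 thrombocytopenia, grade 3 neutropenia or thrombocytopenia lasting more than seven days, grade 3 hyperglycemia, and raised liver enzymes, creatinine, amylase or lipase. If nobody draws blood, a new abnormality of this kind is not found.

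A ±14-day tolerance suits visits three months apart. For visits two weeks apart, its half-width equals the interval. If post-treatment events count toward escalation, missed events can only lower the count, so the error favours escalation. Decisions rest on three to six patients, so one missed event can change the decision at a dose level. The same calendar serves the 10 expansion patients from whom Section 13 estimates the adverse event rate.

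**Working it through.** **1. The plan's own figure.** Section 13 gives escalation probabilities for true DLT rates p. Under the 3+3 rule, P(escalate) = (1-p)³ + 3p(1-p)² × (1-p)³.

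- p = 0.20: 0.512 + 0.384 × 0.512 = 0.709 (plan .71)
- p = 0.30: 0.343 + 0.441 × 0.343 = 0.494 (plan .49)
- p = 0.40, 0.50, 0.60: 0.309, 0.172, 0.082 (plan .31, .17, .08)

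The plan's table is correct. It assumes that every DLT is seen.

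**2. Permitted visit days.** Take EOT as day 0 and the last dose at EOT (Section 5.1). The nominal visits are days 14 and 28, each ±w.

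| w (days) | Visit 1 | Visit 2 | Visits guaranteed on days 1-27 |
|---|---|---|---|
| 14 (plan) | 0-28 | 14-42 | 0 |
| 13 | 1-27 | 15-41 | 1 |
| 7 | 7-21 | 21-35 | 1 |
| 3 | 11-17 | 25-31 | 1 |
| 2 | 12-16 | 26-30 | 1 |

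Visits on days 28 and 42 both comply with Section 10. No symmetric window in the table guarantees two visits, because the second visit is nominally on day 28, one day after the DLT window closes. Narrowing the window alone adds no laboratory test.

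**3. Share of the observation period.** Treatment is 9 weeks × 7 = 63 days, followed by 27 days: 27 / (63 + 27) = 30% of calendar time.

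**4. Residual exposure.** Section 2.2.8.8 gives an effective half-life of 38-49 hours. Five half-lives are 190-245 hours, or 7.9-10.2 days. Cisplatin is last given on day 43 of CRT. With a Monday start and no interruptions or holidays, the 35th fraction falls on day 47, so EOT is about 4 days after the last cisplatin dose. The early part of the period is therefore not free of drug effect.

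**5. What missed DLTs could do (illustration).** The documents give no rate of missed events. Assume that a fraction m of all DLTs goes unseen and that post-treatment DLTs count. The formula in step 1 is then applied to p(1-m).

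| True rate | m = 0 | m = 10% | m = 20% | m = 30% |
|---|---|---|---|---|
| 30% | 0.49 | 0.56 | 0.62 | 0.69 |
| 40% | 0.31 | 0.38 | 0.45 | 0.54 |

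These values of m are assumptions. They are not derived from the 30% in step 3.

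**The case against.** - **Other sections point the other way.** Read alone, the ±2 days of Section 5.12.9 would put the visits on days 12-16 and 26-30, and Section 5.8.1 names a 28-day visit. However, Section 10 is the more specific rule: it ties ±2 days to the treatment phase and ±14 days to follow-up. The 28-day visit sits in text on discontinuation after a dose delay, falls just outside the DLT window and is not in Table 17. Neither section schedules a laboratory test after EOT. What stands is that the sections conflict.
- **A reader might infer that the MTD is biased upward.** The documents do not support that as it stands. If Table 7's heading governs, events after EOT do not enter the escalation count and missing them cannot move the MTD. The bias holds only if Section 5.5 governs.
- **A reader might infer that such events cannot be detected.** That is too strong. Tests may be done when clinically indicated, later visits include an examination and an adverse event query, and febrile neutropenia is symptomatic. Abnormalities already found are followed under Section 5.6, Table 10 and the liver monitoring text in Section 7.1. The accurate statement is that no scheduled test would detect a new, silent one.
- **A reader might take 30% as the share of DLT risk missed.** It is calendar time only; on the half-life figures most BKM120 exposure has gone by days 8-10.
- **Not every patient is affected.** If BKM120 stops early while CRT continues, some or all of the 28 days falls under weekly visits with counts and glucose. Patients stopped for toxicity are followed weekly for four weeks under Section 5.6.
- **Sites may do better than the text requires.** They may, but the primary endpoint should not depend on it.

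**Conclusion.** The concern holds for patients whose last BKM120 dose is at or near EOT and whose laboratory values were normal then. For them Section 10 guarantees zero visits on days 1-27, and Table 17 schedules zero blood tests in that period. The likely loss is limited to new, asymptomatic laboratory DLTs. Its frequency cannot be estimated from the documents.

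The direction of any effect on escalation is clear only if Section 5.5 defines the count, and Section 5.3 and Table 7 leave that open. The point should be fixed because it concerns ascertainment of the primary endpoint and the repair is cheap. It does not show that the design fails.

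**What to change.** 1. In Section 10 and footnote 10, limit the ±14-day window to the monthly and 3-monthly visits.
2. Give the two first-month visits narrow windows, with the second closing no later than day 27: for example day 14 ±3 (days 11-17) and days 24-27. Both visits are then certain to fall inside the DLT window.
3. Add an adverse event query at or after day 27 that covers the whole period since EOT.
4. In Table 17, mark at those two visits the panels that Table 9 uses to define DLTs: hematology, fasting plasma glucose, and chemistry including liver tests, creatinine, amylase and lipase.
5. Reconcile Sections 5.8.1 and 5.12.9 with Section 10. In the same amendment, align the Table 7 heading and the escalation condition in Section 5.3 with the DLT period in Section 5.5.
6. State the remaining limit. Two draws reduce but do not remove the chance of missing a cytopenia of more than seven days: one on days 1-10 falls between EOT and a first draw on day 11, and one on days 12-26 falls between draws on days 11 and 27.

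The visits already exist. The cost is protocol wording, marks in Table 17, less scheduling freedom for two visits, and two routine blood draws per patient.
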